15.2. Informed Consent

The draft ICF must be reviewed by the Sponsor and/or its representative prior to submission to a regional IEC/IRB/HREC for approval. A copy of the ICF approved by the review board must be forwarded to the Sponsor and/or its representative.

The ICF and subject information sheet document the trial-specific information the investigator provides to the subject and the subject's agreement to participate. The investigator or designee will fully explain in layman's terms the nature of the trial along with the aims, methods, anticipated benefits, potential risks, and any discomfort participation may entail. The ICF and subject information sheet must be appropriately signed and dated before the subject undergoes any trial-related procedure. The original and any amended signed and dated ICFs and subject information sheets must be retained in the subject's file at the trial site and a copy of each provided to the subject.

15.3. IEC/IRB/HREC Approvals

The Principal Investigator at each site is responsible for obtaining approval from the appropriate regional IEC/IRB/HREC for the final protocol, Sponsor-approved ICF and subject information sheet if applicable, and any advertisements to recruit subjects. Written approval of these documents must be obtained from the committee before any subject is enrolled at a trial site.

The Principal Investigator is also responsible for the following interactions with the regional IEC/IRB/HREC.

- Obtaining review board approval for any protocol amendments and ICF revisions before implementing the changes
- Providing the review board with any required information before or during the trial
- Submitting progress reports to the review board as required during the conduct of the trial, requesting re-review and approval of the trial as needed, and providing copies of all review board reapprovals and relevant communication to the Sponsor and/or its representative

- Notifying the review board of all serious and unexpected AEs related to the study drug reported by the Sponsor and/or its representative, as required
- Notifying the review board at the end of the trial, in accordance with regional guidelines and regulations

15.4. Subject Compensation for Adverse Effects on Health

The Sponsor and/or its representative will adhere to regional regulations regarding clinical trial compensation to subjects whose health is adversely affected by taking part in the trial.

15.5. Finance and Insurance

Will be described in trial documents.

17.2. Schedule of Events (TransCon hGH Subjects)

Visit	Screening ¹ (-6-0 weeks)	1 ¹ (Week 1)	2 (Week 5)	3 (Week 13)	4 (Week 26)	5 (Week 39)	6 (Week 52)
Trial Day (TransCon hGH subjects)		1 (Predose, Morning)	29 (Predose, Morning)	87-88² (48-72 h post-dose, Morning)	178-179 (48-72 h post-dose, Morning)	269-270 (48-72 h post-dose, Morning)	365 (164-172 h post-dose, Morning)
Visit Window (weeks)				+2	±1	±1	+1
Informed consent	x						
Medical history	x						
Concomitant medication and adverse events		x	x	x	x	x	x
Review of subject diary			x	x	x	x	x
Height and weight measurement	x	x	x	x	x	x	x
Physical examination and vital signs ³	x	x	x	x	x	x	x
Pubertal status	x				x		x
GH-stimulation test(s) ^{4,5}	x						
Assessment of adrenal status ^{6,7}	x						
Karyotype testing ⁸	x						
12-lead ECG ⁹	x	x		x ¹⁰	x		
X-ray of left hand and wrist ⁴	x						x
Sellar MRI ⁴	x						
Fundoscopy ¹¹	x				x		x
Safety laboratory parameters ¹²	x	x	x	x	x	x	x
Fasting required	x	x			x		x
Hormone status ¹³	x	x		x	x		x
Bioanalytical samples ¹⁴	x	x	x	x	x	x	x
Anti-transglutaminase antibodies ⁴	x						
Anti-hGH and anti-PEG antibodies	x ¹⁵	x	x	x	x	x	x
PK/PD Sampling (PK/PD subset) ¹⁶				x ¹⁰			
Drug administration training ¹⁷		x					
Adjustment of dose to body weight				x	x	x	
Study drug administration at site ¹⁷		x	x	x ¹⁶			
Postdose vital signs ³		x ¹⁸		x ¹⁹			
Injection site reaction assessment		x ¹⁸	x	x	x	x	x

Abbreviations: ECG = electrocardiogram; h = hour; hGH = human growth hormone; MRI = magnetic resonance imaging; PEG = polyethylene glycol; PD = pharmacodynamic; PK = pharmacokinetic

- ¹ Following randomization, it is recommended to start V1 within 2 weeks from the time of randomization.
- ² TransCon hGH PK/PD subset subjects will start Visit 3 predose on Day 85.
- ³ Vital signs: Heart rate, blood pressure, respiratory rate and body temperature. Subjects should rest for at least 5 minutes before vital sign assessment.
- ⁴ These diagnostic assessments may be performed prior to Screening within approximately 6 months with proper documentation and approval by the Medical Expert.
- ⁵ Sex hormone priming suggested (but not required) to be performed in girls over the age of 10 and boys over the age of 11.
- ⁶ 8:00 AM cortisol (eg, baseline for GH stimulation test) < 7 µg/dL requires an ACTH stimulation test. 8:00 AM cortisol ≥ 7 µg/dL satisfies inclusion. This assessment may be performed prior to Screening within approximately 3 months with proper documentation and approval by the Medical Expert.
- ⁷ These assessments may be performed prior to Screening within approximately 3 months with proper documentation and approval by the Medical Expert.
- ⁸ Karyotype evaluation in girls. Results prior to Screening may be accepted if well documented; the final decision rests with the Medical Expert.
- ⁹ Subjects should rest for at least 2 minutes before ECG assessment. Screening ECG is locally read; all other ECGs to be read centrally.
- ¹⁰ At predose and 8, 12, 16, 24, 36, 48, 72, 96, 120 and 168 h postdose for TransCon hGH PK/PD subset subjects.
- ¹¹ Should be performed at any time if clinically indicated.
- ¹² Hematology (blood smears will be performed locally for back-up analysis), blood chemistry, lipid and glucose metabolism (fasting glucose, insulin, HbA1c, and OGTT can be assessed locally at any time in case of suspicion of glucose intolerance).
- ¹³ Hormone status: TSH, fT3, fT4, and morning cortisol.
- ¹⁴ Bioanalytical samples for TransCon hGH, hGH, PEG, IGF-1 and IGFBP-3: IGF-1 and PEG will be analyzed at screening and V1 through V6. TransCon hGH, hGH, and IGFBP-3 analysis only at V1 to V6. Screening PEG levels only to be analyzed after randomization.
- ¹⁵ The analysis of the anti-hGH and anti-PEG antibodies may only be conducted after randomization and are not required for eligibility verification.
- ¹⁶ Only for TransCon hGH PK/PD subset subjects.
- ¹⁷ Training on study drug preparation and administration (V1 - during first administration and further as needed).
- ¹⁸ At 15 min, 1 h and 2 h postdose.
- ¹⁹ At 15 min, 1 h, 2 h and 24 h postdose for TransCon hGH PK/PD subset subjects; time point for other subjects as they attend to site.

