	
(Note: Approximately equivalent doses: fluticasone: 264 µg/d; beclomethasone: 504 µg/d; flunisolide 1,000 µg/d; triamcinolone: 1,000 µg/d; mometasone: 211 µg/d; ciclesonide 264 µg/d)
 
17) Major medical conditions and/or presence of contraindication to hGH treatment
 
18) Known or suspected HIV-positive subject
 
19) Known hypersensitivity to the components of the study drug
 
20) The subject and/or the parent/legal guardian are likely to be non-compliant with respect to trial conduct
 
21) Participation in any other trial of an investigational agent within 3 months prior to Screening
 
22) Any other reason that in the opinion of the investigator would prevent the subject from completing participation or following the trial schedule

INVESTIGATIONAL PRODUCT
	
Name: TransCon hGH
 
TransCon hGH is a hGH (human Growth Hormone) prodrug that liberates somatropin as the active ingredient through controlled autohydrolysis resulting in sustained release of unmodified somatropin. TransCon hGH consists of recombinant hGH which is transiently conjugated to a PEG molecule through a (TransCon) linker. This conjugation inactivates hGH, thereby creating the TransCon hGH prodrug. After injection of TransCon hGH, autohydrolysis of the linker occurs in a controlled pH- and temperature-dependent manner whereby unmodified, fully active somatropin is released.
 
TransCon hGH will be provided in glass vials and requires reconstitution with 1 mL sterile water for injection, and will be administered by syringe and needle.

REFERENCE PRODUCT(S)
	
Name: Genotropin (somatropin [rDNA origin] for injection)

TREATMENT REGIMENS
	
TransCon hGH
 
TransCon hGH will be administered as once weekly SC injections of 0.24 mg hGH/kg/week.
 
The administration will preferably be in the morning hours, by the trial staff or by the subjects/parents/legal guardians (under supervision by the trial staff at visits where drug administration is

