	
foreseen). Only if preferred by a parent/guardian/subject, TransCon hGH administration at home may be once weekly in the evening.
 
Genotropin
 
Genotropin (somatotropin [rDNA origin] for injection) will be administered as daily SC injections in a standard dose of 0.24 mg hGH/kg/week.
 
The total weekly dose will be equally split into 7 daily doses of 0.034 mg hGH/kg/day. A commercially approved injection device will be used for administration of the drug.
 
With the exception of Visit 1 where the injection will be performed in the morning by the trial staff or by the subjects/parents/legal guardians (under supervision by the trial staff), daily administration of Genotropin will preferably be in the evening hours by the parents/legal guardians or subjects. Only if preferred by a parent/guardian/subject, Genotropin administration at home may be once daily in the morning. At some trial visits, trial staff will supervise injections.

PLANNED TRIAL SITES
	
Approximately 100 trial sites in approximately 20 countries in North America, Europe, Middle East and North Africa, and Oceania

CRITERIA FOR EVALUATION
	
Efficacy endpoints:
 
Primary efficacy endpoint: Annualized HV at 52 weeks for weekly TransCon hGH and daily hGH treatment groups
 
Secondary efficacy endpoints:
 
 • Annualized HV for the TransCon hGH and the daily hGH treatment group over 52 weeks • Change in HT SDS over 52 weeks for the TransCon hGH and the daily hGH treatment group • Serum IGF-1 and IGFBP-3 levels and IGF-1 SDS and IGFBP-3 SDS; and normalization of IGF-1 SDS over 52 weeks for the TransCon hGH and the daily hGH treatment group 
Safety endpoints:
 
 • Incidence of AEs • Local tolerability (assessed by the subject, the parents/legal guardians and the investigator)

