9.3. Treatments Administered

9.3.1 TransCon hGH

TransCon hGH will be provided as a lyophilized powder, in single-use glass vials, to be reconstituted with 1 mL sterile water for injection. For the composition and characteristics of TransCon hGH, refer to the Investigator's Brochure.

TransCon hGH will be injected SC into the left and right buttock, left and right thigh, and left and right abdomen in the morning hours by the trial staff or by the subject/parent/legal guardian. To minimize local side effects it is recommended to rotate the 6 injection sites in a subsequent manner (eg, right buttock, right abdomen, right thigh, left thigh, left abdomen, left buttock).

During the extension trial planned at the conclusion of this 52-week randomized trial, the plan is to switch from TransCon hGH (ACP-011) in vials to TransCon hGH (ACP-011) in dual chamber cartridges (DCC's), in which TransCon hGH will be supplied as a single dose in a DCC for administration by an Auto-Injector. The DCC presentations will use the 2 compounded solution concentrations also used for the vials in the randomized portion of this trial, 12.1 mg hGH/vial (11.0 mg hGH/mL when reconstituted) and 24.2 mg hGH/vial (22.0 mg hGH/mL when reconstituted), and will be filled with different volumes of the 2 solutions to provide nine presentations with dose increments of approximately 20%. Doses from 3.0 mg hGH to 13.3 mg hGH will be available. When the subjects are dosed with 0.24 ± 0.02 mg hGH/kg/week the associated volumes for injection for each weight range are shown in the table below (Table 1).

For the trial to support the use of the Auto-Injector during the extension phase, the aim is to mimic the dose increments and the associated weight ranges both with respect to injection volume and mg hGH. Therefore, 2 vial presentations will be manufactured; a 12.1 mg hGH/vial (11.0 mg hGH/mL when reconstituted) and 24.2 mg hGH/vial (22.0 mg hGH/mL when reconstituted). Only the drug product at 12.1 mg hGH/vial will be available at start of phase 3. The consequence is that subjects ≥ 24 kg will initially be dosed with a somewhat higher volume, and subjects ≥ 42 kg will initially need 2 injections on the same day using 2 different injection site locations until the 24.2 mg hGH/vial is available during resupply of study drug.

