9.3.2 Genotropin

Genotropin is a lyophilized powder dispensed in a 2-chamber cartridge. For the composition and characteristics of Genotropin, refer to the Summary of Product Characteristics.

Genotropin will be administered as daily SC injections in a standard dose equivalent to 0.24 mg hGH/kg/week. The total weekly dose will be equally split into 7 daily doses of 0.034 mg hGH/kg/day. Genotropin will be administered with an injection device for SC use into the left and right buttock, left and right thigh, and left and right abdomen, recommended in the evening hours (at bedtime), by the subject/parent/legal guardian. Administration will be done at the trial site during the first visit in the morning hours. To minimize local side effects it is recommended to rotate the injection sites in the same manner as TransCon hGH (see [Section 9.3.1](#)).

For specific dosing instructions for both treatment cohorts, please refer to the Pharmacy Manual.

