10.1.2.1 TransCon hGH Cohort (Cohort 1)

- Visits 1 and 2 will be performed on the day of the 1st and 5th dosing (Days 1 and 29), respectively.
- Visits 3, 4 and 5 will be performed 48-72 hours after the 13th, 26th and 39th dose, respectively.
- Visit 6 will be performed 7 days after the last dose (Day 365).

All attempts should be made to adhere to the planned visit schedule. However, in case the subject is not able to attend Visits 3, 4, 5 and 6 during Week 13, 26, 39 or 52, respectively, these visits can be performed with a + 2 week window for Visit 3, meaning either Week 14 or 15, if Week 13 is not achievable; and a ± 1 week window for Visits 4, and 5, meaning either Week 25 or 27, if Week 26 is not achievable or Week 38 or 40, if Week 39 is not achievable; and a + 1 week visit window for Visit 6, meaning Week 53, if Week 52 is not achievable.

Bioanalytical sampling will follow in accordance with the Schedule of Events ([Attachment 17.2](#)). All visits should be in the morning for consistency of auxology measurements, and because subjects should be fasting for Visits 1, 4, and 6.

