10.2.3 Treatment Period

Randomized subjects will receive weekly doses of TransCon hGH or daily doses of Genotropin. The 2 cohorts will be as shown in [Table 3](#).

Table 3
Dose Cohorts

Cohort	Product	Dose Administration
1	TransCon hGH	Once weekly in a dose equivalent to 0.24 mg hGH/kg/week
2	Genotropin	Once daily in a dose equivalent to 0.24 mg hGH/kg/week

hGH = human growth hormone; kg = kilogram; mg = milligram

Following randomization, it is recommended to start the treatment period (Visit 1) within 2 weeks from the time of randomization. During some clinic visits TransCon hGH (Visits 1 and 2) or Genotropin (Visit 1) may be administered in the morning hours by the trial staff or by subject/parents/legal guardians, although Genotropin will generally be administered daily in the evening hours and TransCon hGH will generally be administered weekly in the morning or evening by subjects/parents/legal guardians (or occasionally by the trial staff). Once weekly healthcare services may be offered for the first 4 weeks of treatment to accommodate home administration of TransCon hGH and Genotropin. Extended support may be offered until subjects/parents/legal guardians are comfortable to take over administration of the study drug. Both drugs will be administered SC in the left and right buttock, left and right thigh, and left and right abdomen. It is recommended that injection sites are used successively, being rotated by using a different injection site at each subsequent injection.

In addition to the Screening visit(s), enrolled TransCon hGH and Genotropin subjects will attend a total of 6 trial visits, all in the morning: V1 (Week 1; Day 1; predose, fasting), V2 (Week 5; predose for TransCon hGH subjects; any day during Week 5 for Genotropin subjects), V3 (Week 13; 48-72 hours postdose for TransCon hGH subjects; any day during Week 13 for Genotropin subjects), V4 (Week 26; 48-72 hours postdose for TransCon hGH subjects, fasting; any day during Week 26 for Genotropin subjects, fasting), V5 (Week 39; 48-72 hours postdose for TransCon hGH subjects; any day during Week 39 for Genotropin subjects) and V6 (Day 365 for TransCon hGH subjects [7 days postdose] and Genotropin subjects, fasting).

For the PK/PD subset of TransCon hGH subjects (at least 8 subjects), Visit 3 will span approximately 168 hours following their 13th weekly injection as follows: 1, 2, 3, 4, 5, 6 and 8 days after the dose of that week. The 13th and 14th doses will be given in the clinic.

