6.1.3 Visit Windows

Table 2: Bioanalytical Samples visit windows from Visits 1 to 6

Visit	Time Relative to Dosing, by Visits (Hours)					
	1	2	3	4	5	6
TransCon hGH	predose, morning	predose, morning	48-72h, morning	48-72h, morning	48-72h, morning	164-172h, morning
Week	1	5	13 (+2)	26 (±1)	39 (±1)	52 (+1)
Day	1	29	87-88	178-179	269-270	365
Genotropin	predose, 2h, morning	morning	morning	morning	morning	morning
Week	1	5	13 (+2)	26 (±1)	39 (±1)	52 (+1)
Day	1	29-35	85-91	176-182	267-273	365

Abbreviation: hGH=human Growth Hormone

TransCon hGH Cohort (Cohort 1)

- Visits 1 and 2 will be performed on the day of the 1st and 5th dosing (Days 1 and 29), respectively.
- Visits 3, 4 and 5 will be performed 48-72 hours after the 13th, 26th and 39th dose, respectively.
- Visit 6 will be performed 7 days after the last dose (Day 365).

All attempts should be made to adhere to the planned visit schedule as specified per [Table 2](#). However, in case the subject is not able to attend Visits 3, 4, 5 and 6 during Week 13, 26, 39 or 52, respectively, these visits can be performed with a + 2 week window for Visit 3, meaning either Week 14 or 15, if Week 13 is not achievable; and a ± 1 week window for Visits 4, and 5, meaning either Week 25 or 27, if Week 26 is not achievable or Week 38 or 40, if Week 39 is not achievable; and a + 1 week visit window for Visit 6, meaning Week 53, if Week 52 is not achievable.

Genotropin Cohort (Cohort 2)

- At Visit 1, subjects will be dosed in the morning at the clinic.
- All subjects in the Genotropin cohort will attend Visit 1 fasting with administration of the dose at the investigational site and predose sampling and will have an additional postdose sampling for hGH at 2 hours.
- Visits 2, 3, 4 and 5 will be performed on any day during Weeks 5, 13, 26 and 39, respectively. Preferably, all clinic visits will be in the morning for consistency of auxology measurements. Visit 4 needs to be conducted in the morning hours, since the subject is requested to be fasting. Visit 6 will be performed 1 day after the last dosing (Day 365) in the morning hours, since the subject is requested to be fasting.

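### Evening home dosing of TransCon hGH is allowed, but an evening last dose cannot meet the 164-172 h morning window at Visit 6, and the available protocol and SAP text does not say to move it

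*Protocol*

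**What the plan says.** **Time of dosing.** The Synopsis (Treatment Regimens) states a preference: "The administration will preferably be in the morning hours". It then adds that, where the family prefers, "TransCon hGH administration at home may be once weekly in the evening". Protocol 10.2.3 is more even-handed: "TransCon hGH will generally be administered weekly in the morning or evening by subjects/parents/legal guardians". Protocol 9.3.1 mentions only injection "in the morning hours by the trial staff or by the subject/parent/legal guardian". On-site dosing, which would fix the clock time, is scheduled only at Visits 1 and 2, and for doses 13 and 14 in the PK/PD subset. For detail, the end of Protocol 9.3.2 says: "For specific dosing instructions for both treatment cohorts, please refer to the Pharmacy Manual".

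**Time of Visit 6.** Protocol 10.1.2.1 says "Visit 6 will be performed 7 days after the last dose (Day 365"), and requires visits to be in the morning. The schedule in 17.2 gives "365 (164-172 h post-dose, Morning"), and SAP Table 2 (6.1.3) repeats "164-172h, morning". The +1 week allowance for Visit 6 is in calendar weeks and does not widen the hour window.

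**Analysis.** SAP 11.1.1 summarises serum concentrations at the nominal visit, and its Table 4 labels Visit 6 as 168 h. It also plans accumulation ratios where the data permit, without naming the visits. SAP 8.2 analyses IGF-1 and IGFBP-3 by timepoint. Neither section has a rule based on hours since dose. The mapping windows in SAP Table 3 are in study days.

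**The concern.** A family that doses every week in the evening, as the protocol permits, and attends Visit 6 in the morning seven days after the last dose, as the protocol requires, will be outside the stated sampling window. No choice of calendar day repairs this, because changing the day moves the interval in steps of 24 h.

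At stake is what the TransCon arm's Visit 6 values mean. A sample taken 5-15 h before the end of the dosing interval would be summarised as a 168 h value beside samples that really are at 168 h. The same blood draw supplies the Week 52 IGF-1 and IGFBP-3 values in the by-visit analyses. The daily comparator has no such hour window at Visit 6.

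**Working it through.** **Inputs from the documents**
- Weekly dosing from Day 1; Visit 6 on Day 365; window 164-172 h, morning (Protocol 10.1.2.1 and 17.2; SAP Table 2).
- Visits 3-5 window 48-72 h, with Visit 3 on Days 87-88 (Protocol 17.2).
- For released hGH in healthy subjects: median time to peak 16-36 h, mean terminal half-life 21.8-25.4 h, single-phase decline (Protocol 5.3.1).
- hGH quantification limit 2.00 ng/mL; lower values are set to zero in summaries (SAP 11.1.1).

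**Assumed clock times** (the documents define none): evening dose 17:00-22:00, morning visit 07:00-12:00.

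**1. Reproduce the plan's figure.** Dose 52 falls on Day 1 + 51 × 7 = 358. Then (365 − 358) × 24 = 168 h, the centre of 164-172 h. The plan is consistent when dose and visit are within 4 h of each other by the clock.

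**2. Evening last dose.** Let D be the dose hour, v the visit hour and d the days between. Interval = 24d − (D − v).
- Day 365 (d = 7): 168 − (22 − 7) = 153 h to 168 − (17 − 12) = 163 h.
- Day 366 (d = 8): 192 − 15 = 177 h to 192 − 5 = 187 h.

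**3. Dependence on the assumed hours.** With d = 7, reaching 164 h needs D − v ≤ 4, so even a noon visit needs a dose by 16:00. With d = 8, staying at or below 172 h needs D − v ≥ 20, so even a midnight dose needs a visit by 04:00. Any dose after 16:00 with a visit between 07:00 and noon therefore misses on both days. Extending the evening to 23:00 gives 152-163 h and 176-187 h. Narrowing to doses at 18:00-21:00 and visits at 08:00-10:00 gives 155-160 h and 179-184 h.

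**4. Other visits.**
- Visit 3: an evening dose on Day 85 gives 72 − 15 = 57 h to 72 − 5 = 67 h on Day 88, inside 48-72 h. On Day 87 it gives 33-43 h, so the later scheduled day works. Visits 4 and 5 behave the same way.
- Visit 2: dose 4 is on Day 1 + 3 × 7 = 22 and the predose morning sample on Day 29, so an evening family again has 153-163 h. Visit 2 has no hour window, so this is no violation, but it matters for any ratio of the two troughs.

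**5. Can the effect on hGH be sized?** Carry the half-life from the peak to 168 h:
- Lower end: 2^−((168 − 16)/21.8) = 2^−6.97 ≈ 0.8% of the peak.
- Upper end: 2^−((168 − 36)/25.4) = 2^−5.20 ≈ 2.7% of the peak.

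Reaching 2.00 ng/mL at 168 h would then need a peak of about 73 ng/mL (2.00/0.0273) to 250 ng/mL (2.00/0.008). The documents give no peak concentration, so whether Visit 6 hGH is quantifiable at all is unknown. No decline rate is given for TransCon hGH, PEG, IGF-1 or IGFBP-3.

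**6. Check the remedy.** A visit at v needs a dose between v − 4 and v + 4: 03:00-11:00 for a 07:00 visit and 08:00-16:00 for a noon visit. The overlap is 08:00-11:00. At its extremes, an 11:00 dose with a 07:00 visit gives 164 h, and an 08:00 dose with a noon visit gives 172 h. The preceding interval, from dose 51 at 17:00-22:00 on Day 351, becomes 168 − 14 = 154 h to 168 − 6 = 162 h.

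**The case against.** The strongest reply is that the texts can be reconciled. Evening dosing is a concession and morning is preferred. The window is a requirement, and sites are told to make every attempt to keep to the visit schedule. A family satisfies everything by giving the last dose in the morning, and evening families must already do this once, for the on-site dose at Visit 2. On this view only a reminder is missing, and it may sit in the Pharmacy Manual, Laboratory Manual, Instructions for Use or redacted appendices. This stands in part. Compliance is possible, but only through a step that the available text does not state, and the general call to keep the schedule says nothing about when to inject a week earlier.

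Second, off-window samples can be traced. The diary records dose times (Protocol 9.8). The SAP also plans a dose-timing table (14.3.4.10.3), a protocol-deviation table (14.1.7) and listing (16.2.2.3), and individual concentration listings (16.2.9.7). That is fair. However, none of these flags the samples within the Visit 6 summaries, and the SAP does not say that timing departures count as deviations.

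Third, the plan already pools IGF-1 over a 24 h spread at Visits 3-5, and the largest shortfall here is 11 h below 164 h. This stands as a reason to treat the point as minor.

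Fourth, moving only the last dose would break the match between Visits 2 and 6 for evening families. This also stands, and the fix has to deal with it.

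**Conclusion.** The point holds as a clash between a permission and a sampling window, and it is minor. Under the assumed clock times, an evening-dosing child is sampled at 153-163 h on Day 365 or 177-187 h on Day 366. The miss itself needs only a dose after 16:00 and a visit between 07:00 and noon. It touches the descriptive Visit 6 PK summaries and the by-visit Week 52 IGF-1 and IGFBP-3 results. How many families dose in the evening is not given.

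Three stronger readings are tempting but not supported:
- **That the hGH bias can be quantified.** A reader might apply the half-life to a sample 5-15 h early and get 15% (2^(5/25.4) = 1.146) to 61% (2^(15/21.8) = 1.611) above the 168 h value, then scale by a guessed share of evening families. This presumes quantifiable hGH at 168 h, which the documents do not show, and carries a healthy-subject half-life over to these children. If values are below the limit at both times, the effect is nil.
- **That the accumulation ratios are wrong.** The SAP does not say that Visit 6 enters them, and a consistent evening family has the same interval at Visits 2 and 6.
- **That efficacy conclusions are at risk.** Height velocity does not depend on hours since dose. The IGF-1 average uses Visits 3-5, the SAP 8.3 model uses time since dosing, and the hierarchy in SAP 8.6 contains only the two height velocity tests.

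**What to change.** **Protocol.** In the Synopsis (Treatment Regimens), 9.3.1, 10.1.2.1 and 10.2.3, state that evening home dosing is allowed except that the last dose before Visit 6 is given in the morning. A dose at 08:00-11:00 on Day 358 serves any visit at 07:00-12:00 on Day 365. Put the same line in the Pharmacy Manual and Instructions for Use if it is not already there.

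**SAP 11.1.1 and 8.2.** Derive actual hours since last dose from the diary, and flag Visit 6 samples outside 164-172 h in the Visit 6 PK and Week 52 IGF-1/IGFBP-3 summaries. For any accumulation ratio that uses Visit 2 or Visit 6, report actual hours since dose at both. If dosing is already complete, this part alone still makes the Visit 6 summaries interpretable.

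**Cost.** One sentence and one derived variable from data already collected. For evening families one dosing interval shortens to about 154-162 h. Their Visit 6 sample would also no longer match the 153-163 h timing of their Visit 2 sample, so a Visit 6/Visit 2 comparison has to take actual time into account.
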